2. Discomfort answering research questions and/or providing biological data: Individuals in any study may experience mild and transitory emotional discomfort when answering the questions posed in interviews and on questionnaires, or providing a urine or hair sample. All participants will be informed about these possible risks before signing the consent form. Urine samples collected for research purposes only will not be collected under observation. Samples collected from PATH patients for contingency management will be collected under observation by health center medical assistants. Urine collection staff and research staff will complete a training regarding monitoring and addressing emotional distress among research participants, and a training on the urine and hair collection process which will include suggestions for decreasing participant discomfort. Participants will be told that they can choose not to respond to a question that they find upsetting and can withdraw from participation at any time without negative consequence.
3. Discomfort associated with the treatment interventions: Participants may experience mild and transitory psychological discomfort while participating in the treatment interventions. [name] (Co-I) and the Clinical Supervisor will jointly train the BHCs to monitor patient participants for distress by observing their behavior during their assessment and intervention sessions. This training will focus specifically on helping patients to manage difficult feelings, screening them for potential harm to self and others, and implementing methods to help ensure their physical safety and emotional well-being. If necessary, the BHCs can obtain timely clinical consultation about the participant's distress by contacting the Clinical Supervisor.
4. Possible side effects from MAT: If the patient and his/her provider decide that MAT is appropriate, and the patient is inducted onto medication, then the patient may be at risk for side effects from the MAT. To minimize this risk, the providers trained to deliver MAT in this study will be fully trained on how to appropriately and safely prescribe MAT. Providers will also be trained to thoroughly advise patients about the possible known side effects associated with each medication. Our team will also monitor for frequency of expected and unexpected side effects, intervene when appropriate, and will report side effects of unusual manifestation or unusual frequency to the IRB and DSMB.

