Serious Adverse Events (SAEs) will be defined as 1) death or 2) a life threatening event such as suicide attempt or inpatient hospitalization due to psychiatric distress, drug/alcohol overdose, or severe reaction to a prescribed medication. A component of the study interventions involves referral to specialty treatment, including inpatient hospital-based treatment as appropriate. Admission to hospital-based inpatient substance use treatment will not be defined as an SAE unless, as noted above, it occurs as a result of or in conjunction with clinical worsening, overdose, or complications due to alcohol/drug use. Childbirth, pre-planned elective procedures, and unrelated medical events that require hospitalization will not be considered SAEs. Participants in this study are substance dependent and are thus at risk for clinical worsening. Although we do not believe the study procedures or intervention places participants at increased risk for clinical worsening, we will review and report events of clinical worsening that leads to hospitalization. These events are not anticipated to occur on a regular basis.

Adverse Events (AEs) will be defined as report of coercion to participate in the study; significant discomfort from answering research questions or providing urine/hair samples such that the participant decides to stop their participation; significant discomfort or distress from participating in the intervention; significant discomfort or distress from having process interviews audio-taped; negative side effects due to breach of confidentiality; significant increase in drug/alcohol use or psychiatric symptoms compared to baseline; suicidal ideation; or adverse reactions to MAT. For patients on MAT, we will consider any reaction to the medication that is not a known side effect to be an AE. We will also consider any severe reaction to a medication to be an AE, even if the reaction is a known side effect. We will monitor attrition rates, but drop out from the study will not be reported as an AE. Clinically insignificant

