events (e.g., cold/flu, common headache) are not considered AEs. Participants may have medical and psychiatric problems which may continue during the course of the study. As per the definition of AEs, only significant worsening of baseline medical and psychiatric status or new problems will be reported as AEs. The AEs listed above have been known to occur in prior research with substance dependent populations. However, due to the protections put in place we do not anticipate reports of coercion to participate; significant discomfort from answering research questions, providing urine/hair samples, participating in the intervention, or recorded interviews; or side effects due to breach of confidentiality. Substance abuse and psychiatric disorders are often chronic relapsing diseases, and therefore we anticipate a small percentage of clients will report an increase in drug/alcohol use or psychiatric symptoms during their participation in the study. However, as stated above we will only report these if they are a significant increase from baseline.

All adverse and serious adverse events occurring during the study are documented on a form, reviewed and signed by the Co-PIs or Co-I and reported to TRI and other applicable IRBs. All SAEs are reported to the IRBs within 48 hours of our awareness of the event (24 hours for fatal events). A summary of all SAEs and AEs that occurred during the previous year will be included on the annual progress report to the relevant IRBs.

13. If this study is a chart review, indicate the time frame of data to be collected (from when to when). Also, will the data be collected anonymously (meaning that only aggregate data will be collected, and there will be no names or codes maintained to match the data with the original files)?

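### The SAE definition drops hospitalisations called unrelated without saying who decides or how, and no by-arm safety tabulation exists to recover them

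*Protocol*

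**What the plan says.** Protocol item 12 sets the scope: "Serious Adverse Events (SAEs) will be defined as 1) death or 2) a life threatening event". The examples given for the second limb include admission for psychiatric distress, overdose or a severe drug reaction. Two exclusions follow.

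- Medical admissions: "Childbirth, pre-planned elective procedures, and unrelated medical events that require hospitalization will not be considered SAEs".
- Inpatient addiction treatment: "Admission to hospital-based inpatient substance use treatment will not be defined as an SAE unless, as noted above" it results from, or occurs together with, worsening, overdose or substance-related complications. The protocol explains that referral to such treatment is itself a component of the interventions.

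Item 12 also undertakes that "we will review and report events of clinical worsening that leads to hospitalization".

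The adverse event list in item 12 covers coercion, distress from study procedures, breach of confidentiality, increased substance use or psychiatric symptoms, suicidal ideation and reactions to medication assisted treatment (MAT). It names no general medical event. A few lines later, however, item 12 states that under that same definition "only significant worsening of baseline medical and psychiatric status or new problems will be reported as AEs".

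Forms for adverse and serious adverse events are "reviewed and signed by the Co-PIs or Co-I and reported to TRI and other applicable IRBs", and an annual summary goes to the IRBs. Item 11 adds that the team will "report side effects of unusual manifestation or unusual frequency to the IRB and DSMB". The SAP contains no analysis or table of adverse events by arm.

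**The concern.** Seriousness is normally a matter of what happened, and relatedness a separate judgement about why. Here the second decides the first. An admission for an unexpected medical problem counts only if someone first links it to the study or to substance use, and such a link may not be apparent when the event is first seen.

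The person making that call is not identified, no criteria are given, and neither document mentions blinding. The arms also differ visibly: PATH patients are treated for OUD at the health centre, while Standard Care patients are referred to an outside intensive outpatient programme. Admissions may therefore come to notice, and be attributed, differently in the two arms.

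At stake is whether an imbalance in medical admissions would be recognised as a safety signal, in a trial where PATH offers extended-release naltrexone and buprenorphine.

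**Working it through.** The plan states no admission rate, SAE rate or safety power, so there is no figure to reproduce. The check follows a medical admission judged unrelated through each route in the documents, then illustrates how much the exclusion could matter.

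**Routes**

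1. *SAE (protocol item 12).* Closed by the exclusion.
2. *AE (item 12).* Unclear. The list has no general medical event. The later sentence brings in new problems and worsened medical status, and presents this as following from the list. Both cannot describe the same rule.
3. *Clinical worsening leading to admission (item 12).* Open, but in context it concerns substance dependence. It does not clearly reach, for example, a medical admission with no evident link to use.
4. *MAT side effects (items 11 and 12).* Open, with a stated path to the DSMB, but only once the event has been attributed to the medication.
5. *Service utilisation (item 7; SAP, Secondary Hypotheses).* Open. The NSMOS questionnaire counts hospitalisations and emergency visits outside the assigned treatment at baseline and every follow-up, with no relatedness condition. Hospital days and emergency visits are compared between arms with a Poisson mixed model at months 6, 12 and 18.

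Route 5 is the only one that leads to a between-arm comparison. Its limits as a safety check are:

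- No capture of cause is described. The arm difference in total days is the sum of the difference in substance-related days and the difference in medical days. If the first is negative (the hoped-for benefit) and the second positive, they offset each other and the total can show nothing.
- It depends on completed follow-up. The power section assumes 20% attrition at the final time point, and incarcerated participants are not contacted.
- The model uses months 6, 12 and 18. The recall window is not stated, so reports at months 3, 9 and 15 may not be used.
- It is framed as a benefit hypothesis, and no path to the DSMB or IRB is described.

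**Illustration (admission rates assumed, not from the documents)**

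Inputs: 400 per arm (protocol item 4); two-sided alpha 0.05 (assumed). With p̄ the mean of the two proportions and d their difference:

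- se₀ = √[p̄(1−p̄)·2/400]
- se₁ = √[(p₁(1−p₁)+p₂(1−p₂))/400]
- power = Φ[(d − 1.96·se₀)/se₁]

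For 10% against 16%: p̄ = 0.13, se₀ = 0.0238, se₁ = 0.0237, so power = Φ[(0.06 − 0.0466)/0.0237] = 0.71. If half the admissions are dropped in each arm, the proportions become 5% and 8%, and power = Φ[(0.03 − 0.0342)/0.0174] = 0.41.

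| Assumed risk, SC vs PATH | All counted | Half dropped in each arm | Three quarters dropped in each arm |
|---|---|---|---|
| 5% vs 10% | 77% | 46% | 26% |
| 10% vs 16% | 71% | 41% | 22% |
| 20% vs 28% | 76% | 41% | 22% |

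Unequal attribution could remove the excess altogether. If half are dropped in SC, the share dropped in PATH that equalises the arms is 1 − 0.5·p_SC/p_PATH: 75%, 69% and 64% for the three rows.

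On the scale of a test statistic, 40 against 60 admissions out of 400 gives z = 0.05/0.0234 = 2.14. Half of each, 20 against 30, gives z = 0.025/0.0171 = 1.46.

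**The case against.** A reader might infer that medical admissions never enter any comparison and that an excess in one arm would be invisible. The documents do not support that. NSMOS counts hospitalisations at every follow-up without asking about relatedness, and hospital days and emergency visits are a named secondary outcome analysed by intention to treat. An excess is not removed from the trial's data. What remains is that this outcome does not separate causes and is not safety monitoring.

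A reader might also infer that the investigators who sign the forms are the filter, and that they are unblinded. The sign-off covers events already classed as AEs or SAEs. An admission called unrelated may never get a form, so the filter acts earlier and by someone unnamed. On blinding, the documents are silent. It is fair to ask for it to be specified, but silence does not show that attribution would be biased.

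Other text does capture events. Every death is an SAE without condition. The life-threatening limb is introduced by examples, so it is not a closed list. MAT reactions that are severe, or not already known, are AEs. The exclusion of inpatient addiction admissions has a stated reason, and its wording (together with, as well as resulting from) is broader than strict causation. All of this stands and narrows the gap. It does not close it for an unplanned medical admission that nobody ties to medication or substance use.

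Finally, the numbers rest wholly on assumed rates, and no by-arm test of adverse events is planned, so they describe a comparison that the SAP does not contain. That is correct, and they are offered only to show direction and possible scale. The absence of any such tabulation is part of the problem.

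**Conclusion.** The point holds in this form. Protocol item 12 makes an unassigned judgement of relatedness decide whether a hospitalisation is an SAE. It contradicts itself on whether the excluded admission is then recorded as an AE, and the SAP has no by-arm tabulation of either. The one remaining between-arm comparison can net a medical excess against a substance-related benefit.

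The size cannot be determined from the documents. Under the assumed rates, equal loss of half the admissions takes power from 71–77% to 41–46%, and unequal loss could hide an excess completely. Nothing in the documents shows that attribution would differ by arm. The conclusion rests on the text of the definition and the missing tabulation, not on those figures. It is worth correcting because the cost is small, and admissions not recorded with their cause at the time may be hard to reconstruct later.

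**What to change.** 1. In protocol item 12, record every unplanned hospitalisation in both arms regardless of attribution, with cause, relatedness and expectedness as separate fields. Name who judges them and by what criteria, using existing staff without knowledge of arm where feasible.
2. Flag inpatient addiction referrals that are part of the intervention as their own category, so that they are neither lost nor mixed with medical admissions.
3. Reconcile the AE list in item 12 with the later sentence on new problems and worsened medical status, so that one rule applies.
4. Add to the SAP a tabulation by arm of all these admissions, by cause and by relatedness, for the DSMB and the final report.
5. Leave the existing expedited reporting times for SAEs (48 hours; 24 hours for fatal events) unchanged. Restricting them to related or unexpected events would narrow current reporting and bring the attribution filter back.

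The cost is protocol, SAP and form wording and more events to log. No new visits are needed, because hospitalisations are already asked about at each follow-up.

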Study Title: Patient-Centered Care for Opioid Use Disorders in Federally Qualified Healthcare Centers and Specialty Care Settings

NCT number: Not yet available

Document Date: 11/21/17

Data Analysis Plan

Prior to performing analyses, we will apply standard data screening and cleaning procedures including reviewing the data for data-entry errors, assessing the extent and pattern of missing data, and checking that appropriate assumptions of normality are met. We will employ remedial measures such as power transformations when necessary. We will check that the treatment conditions do not differ at baseline on relevant background variables using analyses of variance (ANOVA) for continuous variables and log-linear models for discrete or ordinal responses. Randomization should minimize the need for covariates to reduce bias in the treatment comparisons, and the primary (i.e., full sample) analyses will not include covariates. In subgroup analyses, relevant covariates will be considered for inclusion as a sensitivity check for randomization and to improve the precision of estimation of the effects [1]. The hypotheses and statistical procedures to analyze the data are listed below. Analyses will be performed using SAS software version 9.1.3.

Primary Hypothesis 1: Clients in the PATH condition will demonstrate higher rates of confirmed substance abstinence (hair and UA verified) during treatment and at follow-up than clients in the SC condition. Confirmed abstinence is the “gold standard” of direct clinical outcomes in SUD research. A mixed effects logistic regression model [2,3] will be used to compare the binary outcome of hair and urinalysis-confirmed abstinence in the two treatment conditions at months 3, 6, 9, 12, 15, and 18. Mixed effects models have advantages of traditional repeated measures approaches in that they allow for missing observations, accommodate measurements made at different time points, provide flexibility in modeling the variance-covariance matrix, and permit the estimation of both group and random patient-specific effects. The model will include terms for treatment condition, time, and their interaction, and the binary baseline abstinence variable along with any other necessary covariates. We will follow the recommendations of Varadhan and Seeger [4] to test heterogeneity of treatment effect (HTE). We have identified two primary subgroup analyses to be performed: (1) setting [IP (n = 400) vs. OP (n = 400)] and (2) type of opioid [heroin (n = 534) vs. prescription (n = 266)]. We will use similar mixed effects logistic regression models (described above) that will additionally include terms for the specific subgroup variable and its interaction with treatment condition. In the event that the interaction is significant, the treatment effect will be estimated separately at each level of the categorical variable that is used to define the subgroups. In addition, we will conduct an *exploratory* subgroup analysis for medication type (agonist vs. antagonist/drug free). We anticipate simple time trends (e.g., linear or quadratic) for the mixed effects models; however, we will use linear spline models in the event complex time trends are observed, such as non-linear trends that cannot be approximated by simple polynomials in time [2]. These analyses will be performed using PROC GLIMMIX.

Primary Hypothesis 2: Clients in the PATH condition will demonstrate greater retention in treatment than clients in the SC condition. Retention is widely considered the leading proxy for clinical effectiveness in SUD treatment. A Cox proportional hazards survival analysis [5,6] will be used to determine whether the rate of dropout differs between the two treatment conditions. The analysis will account for right-censored data as some participants may not experience the event (i.e., treatment dropout, defined as absence from treatment for 30 days) during the period of observation. The analysis will include any necessary covariates. To establish the HTE for this outcome, the survival analysis will be repeated for each primary and exploratory subgroup identified above. Models will include a term for the subgroup variable and its interaction with treatment condition. Again, if the interaction term is significant, the treatment effect will be estimated separately at each level of the categorical variable that is used to define the subgroups. We anticipate that the proportional hazard assumption will be met as we expect the typical pattern of dropout in both groups (i.e., high hazard early, low hazard late). We will conduct standard residual-based analyses to evaluate proportionality and, in the event that the

proportional hazard assumption is violated, we will use extended Cox models that include a time-dependent covariate to model the non-proportionality [7]. The analyses will be performed using PROC PHREG.

Power for the Primary Hypotheses. Power analyses were calculated for the primary hypotheses described above. The power analyses for Primary Hypothesis 1 were calculated following the recommendations of Liu and Wu [8]. The analysis was based on a corrected alpha of .025 (.05/2 primary outcomes), a compound symmetry covariance structure, an estimated abstinence rate of 25% in the SC condition (based on data from our prior study), a correlation between observations on the same patient of .50, and assuming 20% attrition at the final time point. For the smallest subgroup (patients primarily using prescription opioids: $n = 266$; 133 per condition), we will have 80% power to detect an approximately 15% difference in abstinence rates between the conditions (i.e., 25% in control vs. 40% in experimental; OR = 2.0). This projected difference is conservative and based only on the repeatedly demonstrated, similarly scaled differences contingency management yields when compared to standard treatment conditions [9-13]. The smallest detectable differences for the remaining subgroups and the overall sample are as follows using the same specifications: (1) patients recruited from IP setting ($n = 400$): 12%, OR = 1.8, (2) patients recruited from OP setting ($n = 400$): 12%, OR = 1.8, (3) patients primarily using heroin ($n = 534$): 9%, OR = 1.6, and (4) the overall sample ($n = 800$): 8%, OR = 1.5. The power analyses for Primary Hypothesis 2 were calculated following the recommendations of Lakatos [14]. The analysis was based on a corrected alpha of .025, no attrition as chart data will be available for all patients, and estimated dropout rate of 60% in the SC condition [15]. For the smallest subgroup (patients primarily using prescription opioids: $n = 266$; 133 per condition), we will have 80% power to detect a hazard ratio of .59 which corresponds to a difference in survival rates of approximately 18% between the two conditions. The smallest detectable hazard ratio for the remaining subgroups and overall sample are as follows using the same specifications: (1) patients recruited from IP setting ($n = 400$): HR = .65, 15% difference in survival (2) patients recruited from OP setting ($n = 400$): HR = .65, 15% difference in survival (3) patients primarily using heroin ($n = 534$): HR = .69, 13% difference in survival, and (4) the overall sample ($n = 800$): HR = .74, 10% difference in survival. We have chosen to use an alpha level that corrects for the number of primary hypotheses rather than the number of subgroup analyses as the latter approach would substantially increase the likelihood of making a type 2 error [4,16].

Secondary Hypotheses: Relative to those in the SC condition, participants in the PATH condition will demonstrate:

- **Lower rates of service utilization (days of hospitalizations, emergency department visits, residential treatment)**
- **Higher quality of life (Q-LES-Q-SF scores)**
- **Lower rates of HIV risk behaviors (RAB total, sex, and drug risk scores)**

Exploratory Hypotheses: Relative to those in the SC condition, participants in the PATH condition will demonstrate:

- **Improved Employment, Family/Social Functioning, and Psychiatric severity scores on the ASAM Criteria.**

Mixed effects models [2] will be used to compare the treatment conditions on each secondary and exploratory outcome at months 6, 12 and 18. Each model will include terms for treatment condition, time, and their interaction, and the baseline value of outcome measure along with any other necessary covariates. Subgroup analyses similar to those outlined above will be conducted to establish the heterogeneity of the treatment effects. Count data (i.e., service utilization variables) will be analyzed using PROC GLIMMIX specifying a poisson distribution and continuous data (i.e., quality of life, HIV risk scores, and psychosocial severity scores) will be analyzed using PROC MIXED.

Missing values. Missing data will not be an issue for some of the outcomes (i.e., time in treatment). The most important source of missing data in this study is likely to be from participant dropout. We will analyze the data under an intent-to-treat principle in which all participants initially randomized will be included [17]. In addition, mixed effects models will provide valid estimates of intervention efficacy if the missing data are ignorable. We will evaluate the patterns of missing data for each outcome and conduct logistic regression and survival analysis models predicting dropout using client characteristics and accrued measures to determine whether the dropout process is ignorable (i.e. whether missed visits are well explained by observable data). We will examine the impact of missing data by comparing results from models in which missing data are imputed and through pattern-mixture models [18] that examine how responses vary as a function of the pattern of missing data.

Sensitivity analyses . We will conduct a series of sensitivity analyses for the primary hypotheses as recommended by Thabane et al. [19]. We will examine the influence of outliers (identified through boxplots and z-scores) by comparing results from analyses with and without the outlying values. We will examine the impact of protocol non-compliance by comparing the results from the intent-to-treat analyses to analyses in which only participants who received a sufficient dose or different components of the intervention are included; protocol adherence will be represented by weekly medication adherence scores, weekly counseling scores, and combined scores for the sensitivity analyses calculated from TSR and chart review. Furthermore, we will extend the models described above for our primary and secondary outcomes using instrumental variable approaches. Here, the instrumental variable is treatment condition and, under some conditions, will control for unmeasured bias (due to participants self-selecting to comply or not) when estimating the relative effects of the interventions in those who adhere to their assigned intervention. Thus, the results will use data from all subjects who show various degrees of compliance and will yield estimates of the intervention effects that would have been seen in a study with full compliance. For a single overall measure of compliance, the methods of Nagelkerke et al. [20] will be used; if there is sufficient within-subject variation across time in compliance, the longitudinal methods of Small et al. [21] will be used. These sensitivity analyses allow us to determine whether estimates of effect from the primary models can be reported without explicit adjustments for protocol non-compliance. We will examine the impact of our distributional assumptions by comparing results obtained under different distributional assumptions (e.g., parametric vs. non-parametric). We will use multiple imputation and pattern-mixture models to evaluate the impact of missing data as discussed in the prior section. Finally, we will examine the impact of using different definitions of outcomes (e.g., different cutoff points for binary outcomes, objectively verified vs. self-reported substance use) by comparing results obtained from models using different operationalizations of the

outcome variables. These sensitivity analyses will allow us to evaluate the robustness of the study results.

Heterogeneity of treatment effects. The subgroup analyses described above will be used as a test of the heterogeneity of treatment effects. In addition, we have identified three patient characteristics that may be related to treatment effects: psychiatric problem severity (meets pre-determined threshold vs. does not), OUD problem severity (meets pre-determined threshold vs. does not), and housing status (homeless or housed). Each of these variables should negatively impact treatment outcomes, and could suppress differences between conditions. To evaluate the heterogeneity of treatment effects as a function of psychiatric severity, the mixed effects models and survival analyses used to test the primary hypotheses will be modified to include a binary term reflecting psychiatric severity and the interaction of psychiatric severity and condition. A significant interaction would indicate that the effects of the intervention vary as a function of a patient's psychiatric severity (i.e., treatment effects are heterogeneous). If the interaction term is significant, the treatment effect will be estimated separately at each level of the categorical variable that is used to define the subgroups. Similar analyses will be performed for OUD problem severity and housing.

References

7. Allison PD. *Survival analysis using SAS: A practical guide*. SAS Institute; 2010.

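### The SAP bars covariates from the primary analyses yet puts one in the H1 model, and it names no contrast as the H1 test although H1 was powered as a time average

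*SAP*

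**What the plan says.** **Covariates.** The SAP's opening paragraph (Data Analysis Plan) argues that randomisation makes covariates largely unnecessary and concludes that "the primary (i.e., full sample) analyses will not include covariates". It leaves room for them elsewhere: "In subgroup analyses, relevant covariates will be considered for inclusion". Under Primary Hypothesis 1, the full-sample mixed logistic model is then specified with treatment and time terms "and the binary baseline abstinence variable along with any other necessary covariates". Under Primary Hypothesis 2, the Cox model carries a similar sentence: "The analysis will include any necessary covariates". Neither section gives a list or a selection rule.

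**The H1 test.** The model is given as follows: "The model will include terms for treatment condition, time, and their interaction". On the form of time: "We anticipate simple time trends (e.g., linear or quadratic) for the mixed effects models"; otherwise "we will use linear spline models in the event complex time trends are observed". No sentence says which coefficient or contrast decides H1.

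**Power.** The section Power for the Primary Hypotheses (repeated in Protocol item 5) uses alpha .025, compound symmetry, 25% abstinence in Standard Care, "a correlation between observations on the same patient of .50, and assuming 20% attrition at the final time point". The method cited (SAP reference 8) is, by its title, one for a time-averaged difference.

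**Strata.** Protocol item 6 (Main Study) stratifies randomisation by FQHC site and by new or existing patient status. Neither primary model names these factors.

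**The concern.** Two separate gaps leave the confirmatory H1 analysis open.

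First, an analyst who obeys the opening paragraph must drop baseline abstinence, and one who obeys the H1 section must keep it. The open phrase about necessary covariates adds further freedom, because no rule says what counts as necessary.

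Second, a model with a condition-by-time interaction has several candidate tests: the condition coefficient, the interaction, the effect at one month, or the average over visits. The condition coefficient means something different under each coding of time, and it matches the powered quantity only under some of them. Two analysts could therefore follow the SAP and report different H1 p-values, both judged against .025. A choice made after seeing the data would also weaken control of that level.

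A lesser point is that the strata used in randomisation are left out of both primary models. That is conservative rather than biased, and its cost is unknown.

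**Working it through.** **1. The covariate texts side by side.** In the H1 section the word *other* classes baseline abstinence as a covariate. The sentence describes the main model; the subgroup models come later and are described as adding terms to it. Baseline abstinence is therefore a firm clash with the opening paragraph. The looser wording about necessary covariates, for H1 and H2, could be read as meant for subgroups only, so it is a weaker clash.

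**2. What was powered.** Inputs from the SAP: 133 per arm, 25% vs 40%, correlation .50, 20% attrition, six visits. Assumptions: two-sided .025 (sidedness is not stated) and attrition applied at every visit.

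- Effective n per arm = 133 × 0.80 × 6 / (1 + 5 × 0.50) = 182.4.
- Null SE (pooled 32.5%) = √(2 × .325 × .675 / 182.4) = .0490. Alternative SE = √((.25 × .75 + .40 × .60) / 182.4) = .0484.
- Power = Φ((.15 − 2.241 × .0490) / .0484) = 79.6%, against the stated 80%.

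The same formula gives 78.8% for the overall sample at the stated OR of 1.5. A single visit gives only 53.8% for the smallest subgroup. The stated figures therefore rest on a six-visit average.

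**3. What the condition coefficient tests.** Visits are at months 3, 6, 9, 12, 15 and 18 (mean 10.5; sum of squares about the mean 157.5). Assume linear time, a constant effect and complete data.

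- Variance factor of the time average = (1 + 5 × .5) / 6 = .5833.
- Variance factor of the condition coefficient with time zero at t0 = .5833 + (t0 − 10.5)² × .5 / 157.5.
- SE ratio = square root of the second over the first.
- If the time average has 80% power, power = Φ(3.083 / ratio − 2.241), where 3.083 = 2.241 + 0.842. For one-sided .025 it is Φ(2.802 / ratio − 1.960).

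| Time zero at month | SE ratio | Power, two-sided .025 | Power, one-sided .025 |
|---|---|---|---|
| 0 | 1.265 | 57.8% | 60.1% |
| 3 or 18 | 1.143 | 67.6% | 68.8% |
| 6 | 1.054 | 75.3% | 75.8% |
| 9 or 12 | 1.006 | 79.5% | 79.5% |
| 10.5 | 1.000 | 80.0% | 80.0% |

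If time is quadratic, which the SAP also anticipates, the same two-sided calculation gives 26.9% (month 0), 58.9% (month 3 or 18) and 71.9% (month 10.5).

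**4. Check under the model the SAP names.** Random-intercept logistic model with intercept SD 2.888, which gives 25% marginal abstinence and within-patient correlation .50; 400 per arm; Wald test at two-sided .025; 2,000 runs (Monte Carlo SE about 1 point).

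| Scenario | Month 0 | Month 3 | Month 10.5 | Month 18 |
|---|---|---|---|---|
| 25 vs 32.5%, no dropout | 57.2% | 68.2% | 79.6% | 68.2% |
| 25 vs 32.5%, dropout rising linearly to 20% | 54.0% | 65.0% | 78.6% | 63.7% |
| 25 vs 33%, same dropout | 59.8% | 71.3% | 83.1% | 68.1% |
| No effect, no dropout | 2.0% | 2.2% | 2.3% | 2.6% |

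The simulation agrees with the closed form. Each coefficient holds its level if fixed in advance, so what changes is power and the quantity estimated.

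**5. Strata (secondary).** Let R² be the share of person-mean variance that the strata explain; the documents give no value. With stratified randomisation, unadjusted H1 power = Φ(.842 / √(1 − R²)) and adjusted power = Φ(3.083 / √(1 − R²) − 2.241).

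| R² (assumed) | Unadjusted | Adjusted | True alpha, unadjusted |
|---|---|---|---|
| 0 | 80.0% | 80.0% | .0250 |
| 0.5% | 80.1% | 80.2% | .0246 |
| 5% | 80.6% | 82.2% | .0215 |
| 8% | 81.0% | 83.5% | .0194 |

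For H2, 8,000 simulated trials (n = 800, HR .74, four equal sites assumed) gave unstratified vs site-stratified power of 81.8 vs 81.7% with 60% dropout at every site, 81.9 vs 82.2% with dropout of 56 to 64%, and 81.0 vs 81.8% with 50 to 70%.

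**The case against.** The best reply is that the intent is clear enough. H1 speaks of abstinence both during treatment and at follow-up, it is compared over six visits, and the power method is for a time average, so a careful analyst would average. That is fair, and it makes this an unstated contrast rather than a contradictory one. Still, no sentence requires the average.

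The month-0 figure is a worst case. It lies outside the months 3 to 18 window, and codings near the middle lose little, as the table shows. But coding time as months since baseline is an ordinary choice, and starting at month 3 or ending at month 18 already costs about 12 points.

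The firm covariate clash may also have little numerical effect. Screening requires recent opioid use (past month; Protocol item 9) and hair testing looks back about 90 days (Protocol item 7), so few patients may be abstinent at baseline. This stands. No cost is put on that half, and the fix must allow for it.

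On the strata, omission follows a rationale the SAP gives, and the gain from including them is small. That is why the point is secondary.

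Finally, averaging on the logit scale gives a patient-specific odds ratio, while power was stated as a difference in rates. Under the simulated SD, 25 vs 33% is a marginal OR of about 1.48 but a patient-specific OR of about 2.2. The reporting scale should therefore be stated too.

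**Conclusion.** The concern holds and should be fixed before data are seen. The no-covariate rule and the H1 model contradict each other on baseline abstinence. Separately, the quantity powered for H1 is identifiable, but the quantity tested is not specified.

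Depending on how time is coded, reading H1 from the condition coefficient gives anything from no loss to a loss of about 22 points of power (80.0 − 57.8) under linear time. This assumes a constant effect, correlation .50, six visits and two-sided .025; taking .025 as one-sided changes the loss only slightly. If the effect varies over time, the codings also estimate different quantities. None of this shows a stated power figure to be wrong.

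Adding the strata is a small improvement: 0 to about 2.5 points for H1 and at most about 1 point for H2 in the cases assumed.

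**What to change.** 1. Replace the no-covariate sentence and both phrases about necessary covariates with one closed list for the full-sample primary models: FQHC site and new/existing status for H1 and H2, plus baseline abstinence for H1 as already written.
2. State in advance how a term with no usable variation is handled. Baseline abstinence may hardly vary, and new/existing status may be nearly constant too, because Protocol item 9 (Screening) requires that patients not be currently engaged in primary care.
3. Name the primary H1 test as the condition difference averaged over months 3 to 18 at alpha .025. State the sidedness and the scale on which the effect is reported.
4. Fix the form of time, for example month as a six-level factor with an averaging ESTIMATE statement. Keep other time forms as sensitivity analyses.
5. If another contrast is intended, name it and redo the power calculation for it.

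The cost is a few SAP sentences. The strata use about 4 degrees of freedom (3 for the four sites implied by Protocol item 6, Process Evaluation, plus 1 for new/existing). Categorical month uses 8 more than linear month (10 rather than 2, counting the interaction). That is about 12 in all, against 800 patients, and every variable is already collected.
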